17.8.3 Ad libitum pattern of use (Part 1 and Part 3)

The pattern of use during the 14-day *ad libitum* usage periods will be summarized descriptively. This summary will include information on the total number of pouches/loose snus used per day, the estimated usage time per pouch/loose snus, and whether the subjects opened a new can each day. Additionally, the pattern of use data will be listed for both the own brand product period (Part 1) and the selected NP product during Part 3.

Additionally, the subgroup "loose snus users" will be analyzed and presented separately.

17.8.4 Exploratory pharmacokinetics of nicotine in plasma

The nicotine exposure, as measured by baseline-adjusted AUC_{0-inf} and C_{max} based on nicotine plasma concentrations, will be compared between the selected strength NP product and the usual brand snus product, refer to Section 17.7.1.

CONFIDENTIAL 70(76)

Additionally, the subgroup "loose snus users" will be analyzed and presented separately.

17.8.5 Biomarker of exposure in urine (Part 1 and Part 3)

The difference in creatinine-normalized urine concentrations of the different BoE (nicotine and its metabolites, NNN, NNAL, and anabasine) of before and after complete substitution of own brand snus product with a moist NP product for 14 days will be analyzed using the same model as described under Section 17.6.1. The comparison of different BoE (nicotine and its metabolites, NNN, NNAL and anabasine, respectively) between each selected NP in Part 3 vs the subject's own brand in Part 1 will be assessed using the following null (H_0) and alternative (H_1) hypotheses:

$$H_0: \frac{\mu_T}{\mu_R} < 0.8 \text{ or } \frac{\mu_T}{\mu_R} > 1.25$$

 $H_1: 0.8 \le \frac{\mu_T}{\mu_R} \le 1.25$

If the 90% confidence interval for geometric least square ratio falls entirely within the boundaries stipulated by H_1 , equivalence between Part 1 and Part 3 in terms of BoE can be declared, lending credence to the idea of self-titration of nicotine exposure when substituting from an own brand to an NP product.

Additionally, the subgroup "loose snus users" will be analyzed and presented separately.

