Subjects who intend to change their nicotine consumption habit or stop using nicotine-containing products, and/or are pregnant, breastfeeding, or intend to become pregnant during the study, and/or subjects with a history or presence of diagnosed hypertension or cardiovascular disease or other medical condition who may be particularly vulnerable to nicotine exposure, are excluded from participation.

CONFIDENTIAL 23(76)

The nicotine in the NP products is of pharmaceutical grade, same as the nicotine used in nicotine replacement (NRT) products (*e.g.*, gum, lozenges, mouth spray *etc.*). Aside from nicotine, all ingredients used in the NP products are approved for use in food.

The potential adverse effects of the study procedures are expected to be minor and clinically insignificant, based on experience from clinical studies on similar products [8-15]. Notably, previous clinical studies with similar products have reported no adverse events (AEs) other than those likely attributed to nicotine exposure, such as salivation, nausea, and dyspepsia.

The PIs at the study sites will ascertain that adequate facilities and procedures are available to handle emergency situations should they occur during the study. The medical staff at the study sites have extensive experience in clinical studies, and there are adequate procedures in place to handle unexpected and expected adverse reactions in the study subjects.

Aside from the risks related to the IPs, as detailed above, there may also be risks related to the medical devices used in the study during Part 2 (*e.g.*, indwelling venous catheters). However, these devices are used in routine medical care and the risk associated with their use is considered low and ethically justifiable. The repeated blood sampling for PK analysis will be conducted during a 2-week period to give sufficient time between each blood sample occasion. Study specific evaluations and sampling procedures, such as blood pressure measurements using a blood pressure cuff and frequent blood sampling, may cause transient discomfort but the risk is deemed to be low and ethically justifiable. Overall, the combined safety data from previous pre-clinical and clinical studies have not revealed any safety issues that would outweigh the expected benefits of the study.

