6.3.3 Risk/benefit conclusion

The long-term health risks of NPs are not known. Since they contain fewer harmful substances than tobacco-based snus, as they do not contain tobacco, the extensive research available for tobacco-based snus can be used to estimate the long-term health risks of NPs, provided that the nicotine exposure from NPs is not higher than from tobacco-based snus.

Nicotine exposure is primarily dependent on the nicotine content and consumers' usage patterns. The nicotine content in tobacco-based snus and NPs varies greatly and differs between markets (1.5-150 mg per pouch). In Sweden, SIS has established a limit of 20 mg per pouch. NPs with a nicotine content below this threshold are deemed safe for consumer use.

The overarching aim of the study is to achieve a comprehensive understanding of how nicotine content affects actual nicotine exposure, addiction potential, and whether the long-term health risks of NPs can be estimated based on the epidemiological studies available for tobacco-based snus. As the use of NPs has increased significantly in recent years and the products vary greatly in nicotine content, it is important to try to estimate how this affects, for example, long-term cardiovascular health.

In this study, NPs with 3 different nicotine contents will be used, all of which are within the recommended limits and reflect the products commonly used by consumers in Sweden. The

CONFIDENTIAL 24(76)

results of the study can guide the establishment of recommendations and regulations regarding appropriate nicotine limits to restrict the nicotine content of NPs.

In Part 3 of the study, there is a potential risk that some subjects may be exposed to higher levels of nicotine than usual during the 14-day period. However, the nicotine contents in the NP products are below the limits set by SIS and BfR, indicating that the associated risks are expected to be low. Additionally, many consumers already use snus or NP products with high nicotine content, and the study products are similar to those available on the market. Therefore, while there is a risk of increased nicotine exposure, the overall benefit of the study is supported by the low expected risk and the relevance of the study products to existing consumer habits.

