8.1.3 Part 3: Ad libitum use of nicotine pouch product

At Visit 9 (first day of Part 3), the subjects will return to the study site and then the chosen NP product (6 mg/unit, 11 mg/unit or 16.6 mg/unit) will be documented. Based on the subject's reported consumption, they will be provided with the NP product to be exclusively used ad libitum for 14 days (allowed time window: +3 days). During this visit, subjects will undergo interviews regarding any experienced AEs. Subjects will be reminded on how to document their consumption using the eDiary and how to collect used pouches. The subjects will also be provided with collection containers for storing the used pouches and a cooling bag for transportation of the used pouches to the study site.

From the day after *Visit 9*, subjects will completely switch from their own brand snus product to the chosen moist NP product for 14 days, using it *ad libitum*. Subjects will document their consumption once per day via an eDiary throughout the 14-day study period (recording the number of pouches used per day, the estimated usage time per pouch, and whether they opened a new can). Additionally, subjects will collect 4 used pouches on two separate days during the first week (Samples A) and on two separate days during the second week (Samples B), storing them in freezer (\leq -18°C). In total, 8 pouches will be collected per week.

At Visit 10 (14 days after Visit 9) the subjects will return to the study site in the morning. They will bring the collected frozen pouches for extraction analysis. During this visit, subjects will undergo interviews regarding any experienced AEs, the NP product used, and their compliance with the eDiary will be assessed. Additionally, a 24-hour urine collection (allowed time window: ±15 minutes) will begin in the morning. Subject will remain on-site until the following morning, using the selected NP product ad libitum. The urine will be continuously collected during this period for the analysis of BoE.

The subject may leave the study site after completion of the 24-hour urine collection and final assessment of AEs and concomitant medications. This is the end of the subject's study participation.

CONFIDENTIAL 31(76)

Table 8.1-1 Overall schedule of events

Events	CSP section	Visit 1 Screening	Visit 2	Visit 3	Visit 4	Visit 5	Visit 6	Visit 7	Visit 8	Test period	Visit 9	Visit 10
			Pa	rt 1			Part 2				Pa	rt 3
Informed consent	11.3.1	X										
Demographics	11.3.2	X										

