9.6.1 General restrictions

1. Contraception requirements: Subjects of childbearing potential are expected to use contraceptive methods in accordance with inclusion criterion #5 or practice abstinence from heterosexual intercourse (only allowed when this is the preferred and usual lifestyle of the subject) during the clinical study.

2. Tobacco/nicotine products:

In Part 1, subjects are only allowed to use their selected own brand snus product. The subjects are encouraged to follow their regular pattern of use.

In Part 2, subjects shall abstain from any self-administered oral tobacco/nicotine products as well as smoking (cigarettes and e-cigarettes) for at least 12 hours prior to IP use visits and during each IP use visit (Visits 4-8).

In Part 3, subjects are only allowed to use their selected NP product. During this part, subjects can adjust their usage patterns, using the products as much or as little as they wish.

- 3. Mouth related procedures: In Part 2, subjects shall abstain from eating, drinking, or conducting any other mouth related procedure (*e.g.*, tooth brushing) for 30 minutes prior to IP use, during IP use, and for 30 minutes after IP removal (Visits 4-8).
- 4. Drugs of abuse: Subjects shall abstain from any drugs of abuse during the study, *i.e.*, from screening (Visit 1) to the last visit (Visits 10).
- 5. Alcohol: Subjects shall abstain from alcohol for at least 12 hours prior to each visit from screening (Visit 1) to the last visit (Visits 10).
- 6. Blood donation: The subjects must not donate blood or plasma within 1 month of screening until 3 months after the last IP use visit of Part 2 (Visit 8).
- 7. Participation in other clinical studies: The subjects are not allowed to participate in any other clinical study from the screening visit (Visit 1) until the last visit (Visit 10).

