11.2 Electronic patient reported outcome

To fill in the eDiary, the subjects themselves will record data using an electronic patient reported outcome (ePRO) system (ViedocMeTM) linked to the eCRF. The ePRO system includes password protection and internal quality checks.

The subjects will receive eDiary training and instructions at Visit 2 (reminder if needed on Visit 9). The subjects will be instructed to record eDiary data once daily (for the previous calendar day) during the 14-days *ad libitum* use periods of Part 1 and 3. The following data will be collected:

- the number of pouches/portions used
- estimated average use time for each pouch/portion (in minutes)
- if a new box of pouches/loose snus was opened that day (yes/no)

Text reminders to fill in the eDiary will be sent through ViedocMeTM. The site personnel will perform an eDiary compliance check when the subject returns to the site on Visit 3 and 10. All ePRO data will be stored together with the eCRF data.

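### Part 3 analyses the urine biomarkers as complete substitution, but the eDiary does not ask about other products and no stated check verifies exclusive use

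*Protocol*

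**What the plan says.** All of the following is in the protocol.

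- **The instruction.** Section 9.6.1: "In Part 3, subjects are only allowed to use their selected NP product". Section 8.1.3 describes the switch as something that happens: "subjects will completely switch from their own brand snus product to the chosen moist NP product for 14 days".
- **The analysis.** Section 17.8.5 takes the switch as achieved. The contrast is "before and after complete substitution of own brand snus product with a moist NP product for 14 days will be analyzed" with the mixed model of section 17.6.1.
- **The decision rule.** Equivalence is declared "If the 90% confidence interval for geometric least square ratio falls entirely within the boundaries stipulated by H_1", that is, within 0.80 to 1.25. The reading given to that result is "lending credence to the idea of self-titration of nicotine exposure when substituting from an own brand to an NP product".
- **The diary.** Section 11.2 lists three items: the number of units used, "estimated average use time for each pouch/portion (in minutes"), and whether a new box was opened. None concerns own-brand snus or any other nicotine product.
- **Visit 10.** Section 8.1.3 provides for an interview on adverse events and on the pouch product used, an assessment of compliance with the diary, and 24 hours of urine collection on site with use of the selected pouch. Table 8.1-1 adds the return of unused product.
- **The product.** Section 6.3.3 says of the pouches: "Since they contain fewer harmful substances than tobacco-based snus, as they do not contain tobacco". Section 6.3.1 adds: "The nicotine in the NP products is of pharmaceutical grade".
- **Analysis sets.** Sections 17.3.1 and 17.3.2 define a full analysis set and a PK set for Part 2 only.

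**The concern.** Daily snus users are asked to give up their snus, mostly unsupervised, for 14 days. Some may not do so fully. If they do not, the urine contrast estimates the effect of being told to substitute, while the text reports it as the effect of complete substitution.

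What is at stake is the inference that Part 3 exists to support. A subject who keeps some snus in place of pouches stays closer to the Part 1 nicotine level for a reason unrelated to self-titration with pouches. The equivalence rule cannot tell the two apart. The same behaviour would shrink the apparent fall in NNN, NNAL and anabasine. In the regressions of section 17.8.7 it would put biomarker into the urine with no matching recorded intake.

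A later analysis plan can add a sensitivity analysis, but it cannot recover an answer that the diary never requested.

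**Working it through.** **1. Is exclusivity checked anywhere in the stated plan?**

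| Element | What it gives | Tied to an exclusivity check? |
|---|---|---|
| eDiary (11.2) | units, use time, new box | No; no item on other products |
| Visit 10 interview (8.1.3) | pouch product used, diary compliance | No |
| Return of unused product (Table 8.1-1) | a count is possible | No analysis uses it |
| On-site 24-hour urine (8.1.3, 11.6.1.5) | pouch use during that day | Limits use on that day only |
| NNN, NNAL, anabasine (17.8.5, 17.8.7) | outcomes | No |

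**2. Direction of the bias.** The document gives no rate of continued snus use, so the inputs here are assumptions. Let r be the true Part 3/Part 1 ratio under full substitution, and s the continued snus use as a share of Part 1 use.

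- *Urine, snus replacing pouches:* observed ratio = (1 − s)r + s, which moves towards 1. For r = 0.70 and s = 0.2: 0.8 × 0.70 + 0.2 = 0.76. The 0.80 limit is reached at s = (0.80 − 0.70)/(1 − 0.70) = 0.33. From above, r = 1.4 falls to 1.25 at s = (1.4 − 1.25)/(1.4 − 1) = 0.375. A marker that truly falls to 0.05 reads 0.8 × 0.05 + 0.2 = 0.24 at s = 0.2.
- *Urine, snus added to pouches:* observed ratio = r + s. For r = 1.0 and s = 0.2 it is 1.2, away from 1.
- *Diary-based daily exposure (17.8.6), snus unrecorded and displacing pouches:* observed ratio = (1 − s)r. For r = 1.0 and s = 0.2 it is 0.8, away from 1.
- *Extracted amount and fraction per unit* come from the collected pouches, so unrecorded snus does not dilute them. *The PK contrast of section 17.8.4* uses Part 2 plasma data and is not affected.

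**3. Can it change the decision?** The rule concerns the whole 90% interval, so a point estimate is not enough. The document gives no CV for urine. I assume the Part 2 figure of 33% and the 45 evaluable subjects of section 17.2, analysed as pairs.

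- Log-scale SD: √ln(1 + 0.33²) = 0.3215.
- SE of the log ratio: 0.3215 × √(2/45) = 0.0678.
- Half-width: t(0.95; 44 df) × SE = 1.680 × 0.0678 = 0.1139. The lower limit is therefore the estimate × e^(−0.1139) = estimate × 0.892.

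If a fraction q of subjects stays at ratio 1, the geometric mean ratio is r^(1 − q).

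| True r | q | Estimate | Lower 90% limit | Equivalent? |
|---|---|---|---|---|
| 0.85 | 0 | 0.85 | 0.85 × 0.892 = 0.76 | No |
| 0.85 | 0.40 | 0.85^0.6 = 0.907 | 0.907 × 0.892 = 0.81 | Yes (upper limit 0.907/0.892 = 1.02) |
| 0.70 | 0.40 | 0.70^0.6 = 0.807 | 0.807 × 0.892 = 0.72 | No |

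The estimate must reach 0.80/0.892 = 0.897. From r = 0.85 that takes q = 1 − ln 0.897/ln 0.85 = 0.33. From r = 0.70 it takes q of about 0.69.

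**The case against.** **Much of the protection is real.** The urine is collected over 24 hours on site with pouch use only. Subjects must be willing to abstain from other products, they try all three strengths for 2 to 3 days before choosing, and unused product is returned. These make gross non-substitution less likely. The on-site day also makes it less likely that a non-exclusive user stays at the full Part 1 level, as the illustration assumes. How far it protects each marker depends on half-lives that the document does not give. None of these measures shows whether the preceding days were exclusive.

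**A sensitivity analysis may be in the analysis plan.** This stands: its absence from the protocol is not itself a defect. The content of the diary, however, is fixed in the protocol.

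**Stronger readings that a reader might infer.** One is that every Part 3/Part 1 contrast is pulled towards no change. Step 2 shows that this holds only for urine markers when snus replaces pouches. Another is that an observed ratio just above 0.80 already gives false equivalence. The stated rule does not support that: at 0.807 the lower limit is about 0.72. Section 17.8.5 also refers to each selected pouch product. If each strength is tested separately, the groups are smaller and the intervals wider, so false equivalence is harder to reach.

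**Anabasine as an exclusion cut-off.** This is tempting, because the pouches are described as tobacco-free. But anabasine is an endpoint of section 17.8.5 and the dependent variable of Model 5, so removing subjects with high Part 3 values would itself enlarge the apparent fall. The document offers no basis for a threshold and does not state that the pouches are free of anabasine.

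**Conclusion.** The point holds in a limited form. As planned, the urine biomarker contrasts estimate instructed, not verified, substitution, while section 17.8.5 words them as complete substitution and draws a self-titration reading from equivalence. Where snus partly replaces pouches, the error favours that reading and understates falls in the tobacco-related markers. In other patterns of use the direction differs.

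The size is unknown, because no rate of non-exclusive use is given. With CV 33%, 45 pairs and non-exclusive subjects at their full Part 1 level, about a third of subjects would be enough to turn a true ratio of 0.85 into declared equivalence; a true ratio of 0.70 would need about 69%. The decision is therefore vulnerable for moderate departures from 1, and much less so for large ones.

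All affected endpoints are exploratory, the self-titration wording is hedged, and the primary Part 2 comparison is untouched. It is still worth correcting, since the missing information is cheap to collect and cannot be obtained afterwards.

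**What to change.** 1. **Section 11.2:** add one daily eDiary item in both ad libitum parts: any other snus, pouch, tobacco or nicotine product used that day (yes/no, and number). Part 1 needs it too, because the inclusion criteria admit people who previously used both snus and pouches.
2. **Sections 17.8.5 to 17.8.7:** show an analysis restricted to subjects and days with reported exclusive use beside the all-subject analysis. If the two disagree, qualify the self-titration conclusion.
3. **Tobacco-related urine markers:** use them only descriptively, to support or question the self-report, and not as an exclusion cut-off.
4. **Wording of 17.8.5:** say that the all-subject contrast concerns instructed substitution.

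The cost is one diary question and one further set of tables. The exclusive-use subset will be smaller and its intervals wider. Subjects who break the rule may under-report, so the item reduces the uncertainty without removing it.

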Epidemiological data, based on the historical use of traditional Swedish snus in Sweden, shows a highly reduced risk profile for Swedish snus compared to cigarettes. Due to the product category's relative novelty, long-term epidemiological data on NPs is not yet at hand. Given the reduced levels of toxicants in NPs compared to traditional Swedish snus, the epidemiological data on snus can be extrapolated to assess the long-term health risks associated with NP use. The extrapolation is justified as long as the nicotine exposure from NPs does not exceed that from traditional Swedish snus. With a daily consumption of 32.1 g loose snus [2], an extraction of 24 % after one hour of use, and an average nicotine concentration of 0.8 - 1.0%, the daily exposure of nicotine is estimated to be between 62 - 77 mg. NPs, however, have different extraction rates. In this calculation, data from marketed NPs was used. An extraction rate of 39% after one hour of use was estimated, and the average consumption of pouches was found to be between 8.6 - 12.3 per day [3]. A hypothetical nicotine amount of 16.6 mg per pouch would then result in a nicotine exposure of 56 - 80 mg, which is similar to the epidemiologic data for loose snus.

Traditionally, Swedish snus pouch products have contained around 8-10 mg/g of nicotine [4], with the market offering various products with both lower and substantially higher nicotine levels (up to 45 mg/unit). Before the first pouched snus, SMOKELESS, weighed 1 gram, was introduced in 1973, there was only loose snus. More of the famous brands followed with portion-packed versions, including Tre Ankare in 1976, General® in 1985, and Göteborgs Rapé in 1997. Between 1986-2000, the use of loose snus went from being used by 95% to 58% of exclusive snus users.

While most NP products on the Swedish market contain between 1.5 mg and 17 mg of nicotine per pouch, there are concerns about products containing significantly higher amounts. In extreme cases, certain NPs can contain up to 150 mg of nicotine per pouch. This high amount poses serious health risks, especially for new users or those with low nicotine tolerance. Due to these risks and other factors (see below), nicotine limits for NPs have been under discussion. The Swedish Institute for Standards (SIS) set a 20 mg/unit limit in 2020

CONFIDENTIAL 21(76)

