17.1.1 Missing, unused and spurious data

Generally, no imputation of data will be performed. In case of missing start and stop times of AEs that cannot be investigated further, missing data will be imputed according to a worst-case scenario, *i.e.*, start time will be imputed as the closest time point post intake of IP and end time as 23:59, resulting in the longest possible treatment emergent duration of the AE.

Spurious data will be evaluated continuously through data validation (see Section 16) and, if connected to protocol deviations, evaluated case-by-case at the latest prior to declaration of clean file and database lock.

Deviations from the original SAP will be described in the CSR.

Methods for handling of missing, unused, and spurious data will be further specified in the SAP.

[figure not shown]

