17.8.6 Nicotine, NNN and NNK extraction comparison (Part 1 and Part 3)

The difference in contents between unused and used pouches/loose snus portions will be used to calculate the *in vivo* extraction. The calculated extracted amounts of nicotine, NNK, and NNN per pouch/loose snus will be averaged per subject and multiplied with the consumption (number of pouches/loose snus used per day on average) reported in the eDiary over the 14 days *ad libitum* usage period, to receive the daily exposure.

Daily exposure to nicotine, NNK, and NNN will be summarized descriptively and analyzed using the same model and principles as outlined under Section 17.8.5.

Average extracted amounts (mg/unit) and fractions (%) of nicotine, NNK, and NNN will also be summarized descriptively.

Additionally, the subgroup "loose snus users" will be analyzed and presented separately.

17.8.7 Nicotine, NNN and NNK extraction correlation to biomarkers of exposure (Part 1 and Part 3)

Daily exposure to nicotine, NNK, and NNN will be calculated as described under Section 17.8.6. The intake will be correlated with urine concentrations of BoE (nicotine, cotinine, NNN, NNAL, and anabasine) for dose-relationship investigations using linear regression with BoE levels as the dependent variable and daily exposure to nicotine, NNK, and NNN as a continuous explanatory variable in separate models. Subject will be included in the models as a random effect.

CONFIDENTIAL 71(76)

In total the following models will be developed (refer to Table 17.8-1):

Table 17.8-1 Correlation analysis models

Model number:	Dependent variable:	Explanatory variable:
Model 1	Nicotine (Nic) in urine	Daily exposure to nicotine
Model 2	Cotinine (Cot) in urine	Daily exposure to nicotine
Model 3	4-(Methylnitrosamino) -1-(3-pyridyl) -1-butanol (NNAL) in urine	Daily exposure to nicotine
Model 4	N -nitrosonornicotine (NNN) in urine	Daily exposure to nicotine
Model 5	Anabasine in urine	Daily exposure to nicotine
Model 6	3'-trans-hydroxycotinine (OH-Cot) in urine	Daily exposure to nicotine
Model 7	Nicotine equivalents in urine	Daily exposure to nicotine
Model 8	4-(Methylnitrosamino) -1-(3-pyridyl) -1-butanol (NNAL) in urine	Daily exposure to NNK
Model 9	N -nitrosonornicotine (NNN) in urine	Daily exposure to NNN

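### The 0.80–1.25 equivalence test and its self-titration reading also cover NNN, NNAL, anabasine and NNN/NNK daily exposure, where they cannot inform nicotine self-titration

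*Protocol*

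**What the plan says.** Section 17.8.5 compares urine biomarkers after 14 days on the chosen pouch (Part 3) with those after 14 days on own brand snus (Part 1). One pair of hypotheses, with limits 0.8 and 1.25, serves every analyte: "The comparison of different BoE (nicotine and its metabolites, NNN, NNAL and anabasine, respectively) between each selected NP in Part 3" against own brand in Part 1. The decision rule begins "If the 90% confidence interval for geometric least square ratio falls entirely within the boundaries stipulated by H_1", and in that case "equivalence between Part 1 and Part 3 in terms of BoE can be declared, lending credence to the idea of self-titration of nicotine exposure". The conclusion is attached to biomarkers of exposure in general, not to the nicotine markers.

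Section 17.8.6 defines daily exposure as the mean extracted amount per unit (unused minus used content) times the mean number of units per day. It then states: "Daily exposure to nicotine, NNK, and NNN will be summarized descriptively and analyzed using the same model and principles as outlined under Section 17.8.5". The model is that of Section 17.6.1, a mixed model on the natural log scale with subject as a random effect.

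On the products, Section 6.3.3 says of nicotine pouches: "Since they contain fewer harmful substances than tobacco-based snus, as they do not contain tobacco". Section 6.1 argues from the same premise: "Given the reduced levels of toxicants in NPs compared to traditional Swedish snus". Section 6.1 also names oral tobacco as a source of nitrosamines, Section 6.3.1 says the pouch nicotine is of pharmaceutical grade, and the heading of Section 11.6.1.2 calls the nitrosamines tobacco-specific. In Section 7.3, exploratory endpoints 5 and 6 are worded as differences, with no equivalence aim.

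**The concern.** Self-titration, as Section 6.2 describes it, means that users adjust how much they use in order to hold nicotine exposure steady. A ratio near 1 for nicotine, its metabolites or daily nicotine exposure is evidence on that. A ratio near 1 for a constituent that comes from tobacco is not, when the subject is meant to have switched completely to a tobacco-free product.

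The rule as written makes no such distinction. It sets a hypothesis for the tobacco markers that the product description leads one to expect will fail. If it were met, the protocol would read the result as support for nicotine titration. No hypothesis asks whether these markers fell. Separately, the log-scale model in Section 17.8.6 has no value to work with when a subject's extracted NNN or NNK comes out at zero or below.

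At stake is how the report interprets a stated aim of Part 3. The primary and secondary comparisons in Part 2 are not involved.

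**Working it through.** **1. The plan's own figure.** Section 17.2 states 45 evaluable and 53 randomized for the primary comparison, from a CV of 33%, 90% power, a bound of 1.25 and a two-sided 95% CI.
- Log-scale within-subject SD = sqrt(ln(1 + 0.33²)) = 0.3215.
- Normal approximation at a true ratio of 1: n = 2 × 0.3215² × (1.960 + 1.282)² / (ln 1.25)² = 43.6, so 44.
- Noncentral t: 45 with 4(n − 1) degrees of freedom (power 90.6%), 46 with n − 1.
- Dropout: 45 / (1 − 0.15) = 52.9, so 53.

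The stated size reproduces and is not at issue. No power is stated for the tests in Section 17.8.5.

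**2. What the equivalence rule requires.** Assume n = 45 pairs and borrow the 33% CV, which the protocol gives for plasma AUC and not for urine markers.
- Standard error of the log ratio = 0.3215 × sqrt(2/45) = 0.0678.
- Half-width of the 90% CI = 1.680 × 0.0678 = 0.114, a factor of 1.121.
- The observed ratio must therefore lie between about 0.80 × 1.121 = 0.90 and 1.25 / 1.121 = 1.12.

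**3. Chance of declaring equivalence**, from 400,000 simulated trials per cell (n = 45, CV 33%, paired analysis with n − 1 degrees of freedom). The true ratios are assumptions, because the protocol gives none.

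| True Part 3/Part 1 ratio | P(equivalence declared) |
|---|---|
| 1.0 | 0.890 |
| 0.9 | 0.525 |
| 0.8 | 0.050 |
| 0.7 | 0.0002 |
| 0.5, 0.2, 0.05 | 0 |

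With assumed CVs of 20%, 33%, 50% and 80% and n of 15, 45 and 53, the chance is at most 0.003 at a ratio of 0.7 and is 0 at 0.5 or lower. At high CVs or n = 15 it can be low at a ratio of 1.0 too, because the interval itself is wide.

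**4. What each outcome would mean for NNN, NNAL, anabasine and NNN/NNK daily exposure.**

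| Situation in Part 3 | Nicotine markers | Tobacco markers |
|---|---|---|
| Exclusive pouch use, full titration | ratio near 1 | expected to fall, test likely fails |
| Exclusive pouch use, no titration | ratio may move away from 1 | expected to fall, test likely fails |
| Snus use continues | either | ratio moves back toward 1, test may pass |

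The first two rows differ in titration but not in the expected result for the tobacco markers. The third passes for a reason unrelated to titration. In the limiting case where the pouch contributes none of the analyte, the ratio equals the share of Part 1 tobacco exposure that continues. A ratio of 0.80 then requires 80% of it to continue.

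**5. The log scale in Section 17.8.6.** Extracted amount = mean content of unused units − mean content of used units. Both terms are measured. Where a pouch contains little or no NNN or NNK, measurement error alone can make the difference zero or negative. Daily exposure then has the same sign, and its logarithm does not exist.

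**The case against.** The strongest reply is that little harm follows in practice. The endpoints are exploratory. The conclusion is drawn only when equivalence is met, and step 3 shows that this would almost never happen after a substantial fall. The model of Section 17.6.1 already gives a geometric mean ratio with a 95% CI, so a reduction would be visible without a new hypothesis. Sections 6.1 and 6.3.3 make extrapolation from snus epidemiology depend on nicotine exposure not exceeding that of snus. They treat lower toxicant levels as a premise, not as something this test must prove.

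All of this stands, and it sets the weight of the point. It does not remove it. The text fixes a hypothesis and a conclusion for analytes to which they do not apply, and no other section narrows them.

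Three stronger readings are tempting, and the documents do not support them:
- **That Part 3 urine values below the quantification limit will drop out and bias the ratio.** Section 17.1.1 does say "Generally, no imputation of data will be performed", but it also leaves further handling of missing data to the SAP. The only quantification-limit rule in the protocol, in Section 17.7.2, concerns plasma.
- **That the fall will be large, or pouch content close to zero.** No NNN, NNK or anabasine content is given for any product.
- **That failing equivalence would count against self-titration.** Section 17.8.5 attaches no conclusion to failure.

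**Conclusion.** The point holds for the scope of the test. For NNN, NNAL, anabasine and NNN/NNK daily exposure, the 0.80–1.25 rule cannot inform nicotine self-titration in either direction, and the stated reading should not extend to them. The log model also has a gap at zero and negative extracted amounts. How often that would arise cannot be judged from the protocol.

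The expected direction rests on the protocol's own description of the products. It is firmest for NNN and NNK, which are called tobacco-specific, and for NNAL, which Table 17.8-1 pairs with NNK exposure. It is weaker for anabasine, where it rests only on the absence of tobacco in the pouches. Table 17.8-1 pairs anabasine with nicotine exposure alone. The probabilities rest on assumed ratios and a borrowed CV.

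The test remains suitable for nicotine, its metabolites and daily nicotine exposure. Because only exploratory endpoints are affected, this is a should-fix correction. The primary and secondary conclusions and the sample size are unaffected.

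**What to change.** - **Scope (Sections 17.8.5 and 17.8.6).** Limit the 0.80–1.25 test and the self-titration sentence to nicotine, its metabolites and daily nicotine exposure.
- **NNN, NNAL and anabasine in urine.** Report the Part 3/Part 1 geometric mean ratio with its 95% CI and assess reduction, shown by an upper bound below 1.
- **NNN and NNK daily exposure.** Analyse paired differences (Part 3 minus Part 1) on the original scale, so that zero and negative values can be used.

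The cost is a few sentences in two sections, matching SAP text and modest programming. No new data, visits or subjects are needed.
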